6.10. Health Resource Utilization

Healthcare utilization data will also be collected. Information on each hospitalization will be collected utilizing a CRF designed specifically for this purpose. Information to be collected will include, but not be limited to, the reason for hospitalization (eg, disease relapse, AML-related illness, treatment-related AE), and days of hospitalization by treatment setting (inpatient, special care unit). Other disease- and treatment-related forms of healthcare utilization will be collected through routine study activities. These include diagnostic procedures and treatment interventions not requiring hospitalization such as those required for AML-related illness, or for treatment-

related adverse events. Additionally, information on all concomitant medications and resource use associated with treatment administration for AML will be collected.

Healthcare resource utilization information should be collected after a subject signs informed consent through 28 days after the last dose of IP or until the date of last study visit, whichever is later.

[REDACTED]

6.12. Unscheduled Visits

Should it become necessary to repeat an evaluation (eg, laboratory tests, vital signs, etc.), the results of the repeat evaluation should be entered as appropriate in an additional unscheduled visit page of the CRF.

6.13. Discontinuation

The investigator should contact the sponsor or its designee and forward appropriate supporting documents for review and discussion prior to discontinuing a subject. All subjects who have received at least one dose of IP should undergo Treatment Discontinuation procedures when treatment is discontinued. The Treatment Discontinuation procedures include AEs, monitoring for progression of AML and SPM, physical examination, vital signs and weight measurements, ECOG performance status, hematology and serum blood chemistry, serum ferritin level, pregnancy test (FCBP only), concomitant medications, therapies and procedures, transfusions administered, disease status assessment, subsequent AML therapies, IP accountability, HRQoL, and healthcare resource utilization.

If a subject is discontinued during a regular scheduled visit, all Treatment Discontinuation procedures should be complete at that visit. If a procedure had been performed within 7 days of the Treatment Discontinuation visit, it does not need to be repeated. For bone marrow aspirate and bone marrow biopsy, if the procedures have been performed within 15 days of Treatment Discontinuation visit, these procedures do not need to be repeated.

The reason for discontinuation will be recorded in the CRF and in the source document for all randomized subjects, regardless of whether they are dosed or not. Reasons for discontinuation are provided in Section 12.

6.14. Follow-up

All subjects discontinued from protocol-prescribed therapy for any reason will be followed for a period of 28 days following the last dose of IP or until the date of the last study visit, whichever is later, for the collection of AEs, concomitant medications, therapies and procedures, and healthcare resource utilization. Females of childbearing potential should avoid becoming pregnant for 3 months after the last dose of IP and male subjects should avoid fathering a child for 3 months after the last dose of IP.

All subjects discontinued from protocol-prescribed therapy for any reason will also be followed for survival, AML relapse, subsequent AML therapies, and SPM every month for the first year following Treatment Discontinuation and every three months thereafter until death, lost to follow-up, withdrawal of consent for further data collection, or study closure. Documentation such as laboratory or pathology reports, bone marrow and/or peripheral blood reports supporting the AML relapse should be requested and collected. The investigator must make every effort to obtain information regarding the subject's survival status before determining the subject is lost to follow-up. Survival follow-up can be performed via the telephone.

6.15. Extension Phase

Details for the EP are provided in [Appendix K](#).

7. STUDY POPULATION

7.1. Number of Subjects and Sites

This study will enroll approximately 460 subjects, aged 55 or older, diagnosed with AML or AML secondary to prior myelodysplastic disease or CMML, and who have achieved CR/CRi following induction with or without consolidation chemotherapy. In addition, subjects should not be eligible for allogeneic bone marrow or stem cell transplantation.

The study will be conducted at approximately 180 clinical sites across the world.

7.2. Inclusion Criteria

Subjects must satisfy the following criteria to be enrolled in the study:

1. Male or female subjects ≥ 55 years of age at the time of signing the ICD;
2. Newly diagnosed, histologically confirmed *de novo* AML or AML secondary to prior myelodysplastic disease or CMML;
3. Should have undergone induction therapy with intensive chemotherapy with or without consolidation therapy;
4. Must have achieved first CR/CRi status within 4 months (± 7 days) prior to randomization, as evidenced by the following:

Complete Remission (CR)	Complete Remission with Incomplete Blood Count Recovery (CRi)

 • $< 5\%$ blasts in bone marrow • absence of blasts with Auer rods • absence of extramedullary disease • independent of blood transfusions • peripheral neutrophil count $> 1.0 \times 10^9/L$ • platelet count $\geq 100 \times 10^9/L$ 	
 • $< 5\%$ blasts in bone marrow • absence of blasts with Auer rods • absence of extramedullary disease • independent of blood transfusions • peripheral neutrophil count $< 1.0 \times 10^9/L$ or platelet count $< 100 \times 10^9/L$

5. ECOG performance status of 0, 1, 2 or 3 ([Appendix B](#));
6. Adequate bone marrow function based on ANC $\geq 0.5 \times 10^9/L$ and platelet counts $\geq 20 \times 10^9/L$
7. Adequate organ function, defined as:
 - Serum bilirubin ≤ 1.5 times the upper limit of normal (ULN);
 - Serum aspartate aminotransferase (AST) and alanine aminotransferase (ALT) ≤ 2.5 times the ULN;
 - Serum creatinine ≤ 2.5 times the ULN;

8. FCBP¹ may participate, providing they meet the following conditions:
 - Agree to practice abstinence; or
 - Agree to use at least two effective contraceptive methods (oral, injectable, or implantable hormonal contraceptive; tubal ligation; intra-uterine device; barrier contraceptive with spermicide; or vasectomized partner) throughout the study, and for 3 months following the last dose of oral azacitidine; and
 - Have a negative serum pregnancy test (sensitivity of at least 25 mIU/mL) at screening; and
 - Have a negative serum or urine pregnancy test (Investigator's discretion) within 72 hours prior to starting study therapy in the double-blind treatment phase (note that the screening serum pregnancy test can be used as the test prior to starting study therapy in the double-blind treatment phase if it is performed within the 72-hour timeframe).
9. Male subjects with a female partner of childbearing potential must agree to practice abstinence or to the use of a physician-approved contraceptive method throughout the course of the study and avoid fathering a child during the course of the study and for 3 months following the last dose of azacitidine;
10. Understand and voluntarily sign an ICD prior to any study related assessments/procedures are conducted;
11. Able to adhere to the study visit schedule and other protocol requirements;
12. Ability to swallow study medication.

7.3. Exclusion Criteria

The presence of any of the following will exclude a subject from enrollment:

1. Suspected or proven acute promyelocytic leukemia (FAB M3) based on morphology, immunophenotype, molecular assay, or karyotype; or AML with previous hematologic disorder such as chronic myeloid leukemia or myeloproliferative neoplasms, excluding MDS and CMML;
2. AML associated with inv(16), t(8;21), t(16;16), t(15;17), or t(9;22) karyotypes or molecular evidence of such translocations;
3. Prior bone marrow or stem cell transplantation;
4. Have achieved CR/CRi following therapy with hypomethylating agents;
5. Received therapy with hypomethylating agents for MDS and went on to develop AML within four months of discontinuing the therapy with hypomethylating agents;
6. Proven central nervous system leukemia;
7. Candidate for allogeneic bone marrow or stem cell transplant at screening;

¹ A woman of childbearing potential is a sexually mature woman who 1) has not undergone a hysterectomy (the surgical removal of the uterus) or bilateral oophorectomy (the surgical removal of both ovaries) or 2) has not been naturally postmenopausal for at least 24 consecutive months (ie has had menses at any time during the preceding 24 consecutive months).

8. Diagnosis of malignant disease within the previous 12 months (excluding basal cell carcinoma of the skin without complications, “in-situ” carcinoma of the cervix or breast, or other local malignancy excised or irradiated with a high probability of cure);
9. Unstable angina, significant cardiac arrhythmia, or New York Heart Association (NYHA) class 3 or 4 congestive heart failure ([Appendix D](#));
10. Uncontrolled systemic fungal, bacterial, or viral infection (defined as ongoing signs/symptoms related to the infection without improvement despite appropriate antibiotics or other treatment);
11. Known active viral infection with known human immunodeficiency virus (HIV) or viral hepatitis type B (HBV) or C (HCV);
12. Known or suspected hypersensitivity to azacitidine or mannitol;
13. Use of any other experimental drug or therapy within 28 days prior to Day 1 of Cycle 1;
14. Unwilling or unable to complete patient reported outcome assessments without assistance or with minimal assistance from trained site personnel and/or caregiver;
15. Any condition, including the presence of laboratory abnormalities, which places the subject at unacceptable risk if he/she were to participate in the study;
16. Any significant medical condition, laboratory abnormality, or psychiatric illness that would interfere or prevent the subject from participating in the study;
17. Any condition that confounds the ability to interpret data from the study;
18. Any condition causing an inability to swallow tablets;
19. Any condition that would impair absorption of the study medication (i.e. short gut, malabsorption syndrome).

7.4. Inclusion and Exclusion Criteria for EP

Refer to [Appendix K](#) for Inclusion and Exclusion Criteria in the EP of the study.

8. DESCRIPTION OF STUDY TREATMENTS

8.1. Description of Investigational Product(s)

8.1.1. Azacitidine and Placebo

Celgene Corporation will supply azacitidine 150- and/or 200-mg tablets and matching placebo tablets for oral administration. Each tablet is formulated using excipients that are generally regarded as safe and are used in marketed drug products.

All tablets will be packaged in blister cards. Only sufficient IP for one cycle of treatment will be provided to each subject at the start of each treatment cycle. All tablets should be swallowed whole and should not be broken or chewed.

No modification of tablets is necessary to preserve blinding as both placebo and azacitidine tablets are identical in appearance.

Shelf-life evaluation of the intact blister card is ongoing. Study drug will be monitored for stability for the duration of the study.

8.1.2. Best Supportive Care

Best supportive care may be used in combination with study treatment as deemed necessary. Best supportive care in both treatment arms will include, but not limited to RBC and platelet transfusions, use of an ESA, antibiotic, antiviral, and antifungal therapy, nutritional support (Section 9.1), and granulocyte colony stimulating factors (G-CSFs) for subjects experiencing neutropenic infections (Section 9.1), thus the risk of not providing subjects with appropriate care is minimized, while providing the potential benefit of maintaining CR/CRi status.

8.2. Treatment Administration and Schedule

8.2.1. Investigational Product Treatment Schedule

Following screening, eligible subjects will be randomized to receive 300 mg oral azacitidine or matching placebo QD for 14 days of each 28-day treatment cycle as described in Section 8.2.3. In the event of toxicity, dose and schedule may be modified (see Section 8.2.5). Subjects may continue to receive the protocol-prescribed therapy for as long as they benefit from the treatment or until treatment is discontinued for reasons detailed in Section 12. The Investigator should contact the Medical Monitor and forward appropriate supporting documents for review and discussion prior to discontinuing a subject.

8.2.2. Investigational Product Dispensation

Investigational product will be dispensed on Day 1 of each treatment cycle. Only 1 cycle of IP will be dispensed to the subject on Day 1 of each treatment cycle.

The subject may not receive IP for each treatment cycle until all Day 1 procedures have been completed and all IP from the previous cycle are to be accounted for (where applicable).

For FCBP subjects, a pregnancy test must be verified negative when performed within 72 hours prior to IP administration on Day 1 of Cycle 1.

8.2.3. Investigational Product Administration

Investigational product administration will be accurately recorded including, but not limited to, date of administration, dose and any changes in dose administration (eg, interruption or reduction in dose due to an adverse event).

Investigational product is scheduled to be taken on the first 14 days of each 28-day treatment cycle, unless there has been a schedule modification of IP administration due to disease relapse or toxicity. On PK sampling days, IP will be administered by the study site personnel in the clinic. Subject will self-administer all other IP doses in the treatment phase.

Antiemetic medication (not supplied by the sponsor) may be taken 30 minutes prior to IP administration. Subject will ingest IP with approximately 240 mL (8 ounces) of room temperature water. Investigational product may be taken on an empty stomach or with food. If IP is taken in the morning, subjects may consume their usual breakfast before or after administration. The breakfast meal should not exceed approximately 600 calories; however, the actual calorie will not need to be measured or recorded. If a meal other than breakfast is consumed, a light meal (not more than 25% of a subject's usual daily calories) may be eaten before or after administration.

Refer to Section 8.6 for details regarding IP accountability.

8.2.4. Missing Doses

All efforts should be made to administer IP on all of the scheduled days of each 28-day treatment cycle. Any missed doses during that period should not be taken after the last scheduled day of administration but should be returned by the subject for IP accountability. Any vomited doses should not be repeated. Treatment should resume on the next scheduled day.

8.2.5. Dose Modifications for Toxicity

Subjects should be monitored for toxicity using the National Cancer Institute Common Terminology Criteria for Adverse Events (NCI-CTCAE), Version 4.0, as a guide for the grading of severity.

If a certain level of toxicity is observed and considered by the investigator to be at least possibly related to treatment, IP dosing may be interrupted, delayed or modified. The Investigator is encouraged to contact the Medical Monitor prior to any treatment adjustment.

A maximum of one dose reduction to a daily dose of 200 mg is permitted in the event of toxicity. If toxicity persists, a maximum of one treatment schedule modification from 14 to 7 days (21 days to 14 days for those subjects whose dose schedule has been extended due to disease progression) is permitted in the event of continuing toxicity that does not respond to dose reduction. The decision to modify a subject's treatment schedule from 14 to 7 days (21 days to 14 days for those subjects whose dose schedule has been extended due to disease progression) should first be discussed with the Medical Monitor or designee. Subjects should not receive less than 200 mg IP or be scheduled to receive treatment for less than 7 days.

Subjects who have their IP dose reduced or treatment schedule modified may return to their original dose and/or schedule in a step-wise fashion upon discussion and agreement between the investigator and the Medical Monitor provided that the increased dose or treatment schedule is

tolerable and at least two additional treatment cycles have occurred since the dose reduction or treatment schedule modification. The treatment schedule should first be increased from 7 to 14 days, followed by a dose escalation step from 200 to 300 mg.

Dose Modification for Febrile Neutropenia \geq Grade 3

Any subject who experiences febrile neutropenia (two consecutive readings of body temperature $> 38.0^{\circ}\text{C}$ for 2 h and an absolute neutrophil count $< 0.5 \times 10^9/\text{L}$) can continue to receive IP uninterrupted at the discretion of the Investigator. If the febrile neutropenia episode persists for ≥ 4 days despite adequate/maximal antibiotic, antiviral and/or antifungal therapy, IP should be temporarily discontinued until the fever has resolved and the ANC has improved or stabilized as assessed by the Investigator. Treatment with IP at the same dose should resume no earlier than 3 days following the resolution of the fever. If a subject experiences febrile neutropenia in 2 consecutive cycles, the steps noted above should be followed, but the IP dose should be reduced to 200 mg upon resumption of treatment with IP. A treatment schedule modification from 14 to 7 days (21 days to 14 days for those subjects whose dose schedule has been extended due to disease progression) of treatment may be warranted if a subject experiences regular episode of febrile neutropenia that are deemed by the Investigator to be related to IP.

Dose Modification for Diarrhea \geq Grade 3

It is recommended that subjects experiencing diarrhea be managed according to the guidelines provided in [Appendix I](#). Antidiarrheal medication may be administered as prophylaxis against diarrhea and for treatment of any AEs of diarrhea. Dose modifications for diarrhea are summarized in Section [8.2.5](#). In patients not having problems during the first two cycles, the treating physician may discontinue use of antiemetic medications.

Dose Modification for Nausea and Vomiting \geq Grade 3

A serotonin (5-HT³) receptor antagonist (eg, ondansetron) (or other comparable medication) should be administered as an antiemetic approximately 30 minutes prior to administration of IP. Antiemetic medication(s) should be administered for treatment of any AEs of nausea and/or vomiting. If there has been no nausea and/or vomiting during the first two cycles, Investigator may choose to omit antiemetic as required, provided this is clearly documented in the CRF. Dose modifications for nausea and vomiting are summarized in Section [8.2.5](#).

Dose Modification for Renal Dysfunction and Abnormal Serum Electrolytes

If unexplained elevations of BUN and/or serum creatinine ($> 20\%$) occur (per Investigator), the next cycle of treatment should be delayed until values return to baseline and the dose should be reduced to 200 mg in the next cycle of treatment. A schedule modification from 14 to 7 days (21 days to 14 days in those subjects whose dose schedule has been extended due to disease progression) can be made if the elevation in BUN and/or creatinine recurs in the subsequent cycle. Should similar unexplained renal disturbances subsequently persist or recur during the next cycle of treatment, study treatment should be discontinued.

Dose Modification for Other Treatment-Related Non-Hematologic Toxicity \geq Grade 3

Any subject who experiences a treatment-related non-hematologic toxicity Grade 3 or higher that is an escalation from baseline status (prior to first IP dose) should temporarily discontinue IP treatment until the toxicity returns to Grade 2 or lower. Dose modifications for Grade 3 or higher non-hematologic toxicity are summarized in Section [8.2.5](#).

Dose Modification for Weight Change

No dose adjustment should be made for weight loss or gain alone; however, the reason for weight loss (eg, significant nausea, vomiting, anorexia, etc.) or weight gain (eg, peripheral edema) should be investigated and may require a dose modification as specified in Section 8.2.5.

Table 2: Guidelines for Dose Modifications

NCI-CTCAE Toxicity Grade	Action
Febrile Neutropenia (≥ Grade 3)	
 • Continue IP at the discretion of the Investigator 
 – If episode persists for ≥ 4 days despite adequate / maximal antibiotic, antiviral and/or antifungal therapy, IP should be temporarily discontinued until the fever has resolved. – Resume IP at the same dose after the fever has resolved and the ANC has improved or stabilized (as assessed by the Investigator). IP should not be resumed for at least 3 days following resolution of fever. • If a subject experiences febrile neutropenia in 2 consecutive cycles, the steps noted above should be followed, but the IP dose should be reduced to 200 mg upon resumption of treatment with IP. • If subject continues to experience febrile neutropenia episodes that are deemed to be related to IP by the Investigator, a treatment schedule modification from 14 to 7 days (21 days to 14 days for those subjects whose dose schedule has been extended due to disease progression) of treatment may also be warranted. (Treatment schedule modification requires prior discussion with Medical Monitor).
Diarrhea (≥ Grade 3)	
 • Interrupt IP and provide adequate/maximum medical intervention • Resume IP at same dose when toxicity resolves to ≤ Grade 1 • If event reoccurs upon re-challenge or during next treatment cycle, reduce IP dose to 200 mg. • If event reoccurs at same intensity once dose is reduced to 200 mg, follow the steps above and modify treatment schedule from 14 to 7 days (21 days to 14 days for those subjects whose dose schedule has been extended due to disease progression) of IP administration. (Treatment schedule modification requires prior discussion with Medical Monitor).

Table 2: Guidelines for Dose Modifications (Continued)

NCI-CTCAE Toxicity Grade	Action

Nausea and/or Vomiting (≥ Grade 3)
	
 • Interrupt IP and provide adequate/maximal medical intervention • Resume IP at same dose when toxicity resolves to ≤ Grade 1 • If event reoccurs upon re-challenge or at same intensity during next treatment cycle, reduce dose to 200 mg • (Treatment schedule modification requires prior discussion with Medical Monitor).

Renal Dysfunction
	
 • For unexplained elevations of BUN and/or serum creatinine (> 20%), hold IP, if this is apparent during the IP administration phase and/or delay the start of the next cycle of treatment until values return to baseline (± 20%). Reduce IP dose in the next cycle of treatment to 200 mg. • Discontinue IP if similar unexplained renal and/or electrolyte disturbances subsequently persist or recur during the next cycle of treatment. • (Treatment schedule modification requires prior discussion with Medical Monitor).

Other ≥ Grade 3 non-hematological treatment-related AEs
	
 • Interrupt IP dosing and provide medical intervention as appropriate • Resume IP at same dose when toxicity resolves to ≤ Grade 2 • If event reoccurs upon re-challenge or at same intensity during next treatment cycle, reduce IP dose to 200 mg • If event reoccurs at same intensity once dose is reduced to 200 mg, follow the steps above and modify treatment schedule from 14 to 7 days (21 days to 14 days for those subjects whose dose schedule has been extended due to disease progression) of IP administration. (Treatment schedule modification requires prior discussion with Medical Monitor).

AE=Adverse Event; ANC=Absolute Neutrophil Count; CTCAE=Common Terminology Criteria for Adverse Events; NCI=National Cancer Institute; IP=Investigational Product.

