8.2.6. Dose and Schedule Adjustment in Subjects with AML Relapse/Progression

In subjects on study who have subsequent evidence of AML relapse with blasts > 5% either in the peripheral blood count or bone marrow, and provided the blasts are no greater than 15% in the blood or bone marrow, escalation of the dosing regimen (dose and/or schedule) can be implemented as follows (provided it is in the best interest to do so as judged by the Investigator):

- Subject currently on blinded treatment of oral azacitidine 300 mg or placebo QD for 14 days - escalate schedule to oral azacitidine 300 mg or placebo QD for 21 days
- Subject currently on blinded treatment of oral azacitidine 200 mg or placebo QD for 14 days - escalate dose schedule, as a first step, to oral azacitidine 200 mg or placebo QD for 21 days and then escalate dose to oral azacitidine 300 mg or placebo QD for 21 days
- Subject currently on blinded treatment for oral azacitidine 200 mg or placebo QD for 7 days - escalate dose schedule, as a first step, to oral azacitidine 200 mg or placebo QD for 14 days and then escalate dose to oral azacitidine 300 mg or placebo QD for 14 days

In cases where relapse is noted within a week of starting the next cycle, and there is a desire to escalate the dose schedule during the cycle, contact the Medical Monitor to discuss this, in order to obtain the additional required IP.

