### 9.3. Dose Adjustments

Dose adjustments (including dose escalation and dose reduction), as reported in the dose exposure CRF page, will be summarized by treatment arm and include the following:

- Any dose adjustments;
- Dose adjustment due to AE;
- Dose adjustment due to AML relapse/progression;
- One dose reduction;
- Two dose reductions;
- Dose escalation (to 300mg × 21 days).

Dose adjustment is defined as subjects who have reported at least one dose adjustment in the dosing CRF page. One dose reduction is defined as subjects have reduced assigned dose from 300mg × 14 days to 200mg × 14 days. Two dose reduction is defined as subjects have reduced assigned dose from 300mg × 14 days to 200mg × 14 days, and then from 200mg × 14 days to 200mg × 7 days. Dose escalation is defined as subjects who have received at least one assigned dose of 300mg × 21 days.

In addition, time to first dose adjustment due to AE, time to first dose adjustment due to AML relapse/progression, reason for first dose adjustment and reason for first dose escalation will also be summarized.

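### SAP 9.3 defines its one- and two-reduction rows only on the 14-day schedule, so toxicity steps taken from the 21-day schedule in Protocol 8.2.5 are missed or miscounted in those rows

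*Protocol*

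**What the plan says.** **Protocol.** Section 8.2.6 gives the route onto the longer schedule. For a subject on 300 mg for 14 days whose blasts exceed 5% but not 15%, the investigator may "escalate schedule to oral azacitidine 300 mg or placebo QD for 21 days". A subject on 200 mg for 14 days may first go to 200 mg for 21 days and then to 300 mg for 21 days.

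Section 8.2.5 then sets the toxicity steps. The dose step is stated without reference to a schedule: "A maximum of one dose reduction to a daily dose of 200 mg is permitted in the event of toxicity". The schedule step has two forms: "one treatment schedule modification from 14 to 7 days (21 days to 14 days for those subjects whose dose schedule has been extended" because of progression). The second form recurs in the febrile neutropenia and renal text of the same section. It recurs again in Table 2, where the rows for diarrhea and for other Grade 3 or higher non-hematological events repeat "21 days to 14 days for those subjects whose dose schedule has been extended due to disease progression) of IP administration".

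**SAP.** Section 9.3 defines the first reduction row by named regimens: "One dose reduction is defined as subjects have reduced assigned dose from 300mg × 14 days to 200mg × 14 days". The second row requires that step "and then from 200mg × 14 days to 200mg × 7 days". No other path is named. The same section has broader rows. One rests on a general rule, "Dose adjustment is defined as subjects who have reported at least one dose adjustment in the dosing CRF page", and another is headed "Dose adjustment due to AE". SAP Section 15, which lists changes from the protocol's statistical section, does not mention dose-reduction counting.

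**The concern.** The two reduction rows are the only place where the SAP reports how many steps down a subject needed. They are written around the starting regimen and leave out the steps that the protocol provides for subjects whose schedule was extended. The SAP otherwise takes care to describe the 21-day regimen: it has an escalation row, separate exposure summaries and dedicated adverse event tables. How often that regimen had to be stepped down is a basic tolerability result. The regimen carries 1.5 times the drug per cycle (300 mg x 21 = 6300 mg against 300 mg x 14 = 4200 mg). A clinical study report that follows the definitions literally would show step counts that do not correspond to the protocol's own scheme, with nothing to tell the reader so.

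**Working it through.** The plan gives no figure for this point, so there is nothing to reproduce. The check applies the SAP 9.3 definitions literally to paths that Protocol 8.2.5 and 8.2.6 allow. Regimens are written as mg x days per 28-day cycle.

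| Path | Toxicity steps under Protocol 8.2.5 | SAP one-reduction row | SAP two-reduction row | Any-adjustment row |
|---|---|---|---|---|
| 300x14 > 200x14 | 1 (dose) | yes | no | yes |
| 300x14 > 200x14 > 200x7 | 2 (dose, schedule) | yes | yes | yes |
| 300x14 > 300x21 > 200x21 | 1 (dose) | **no** | no | yes |
| 300x14 > 300x21 > 200x21 > 200x14 | 2 (dose, schedule) | **no** | **no** | yes |
| 300x14 > 200x14 > 200x21 > 200x14 | 2 (dose, schedule) | yes | **no** | yes |

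The moves up to 21 days are relapse-driven and are not counted as toxicity steps. The SAP does not say whether a subject in the two-reduction row also stays in the one-reduction row. The table assumes so; making the rows exclusive does not change the last three lines.

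The first two paths are counted correctly. The third and fourth are missed by both rows. The fifth is credited with one step because of its earlier 14-day reduction, and its later 21-to-14-day step is lost.

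Next, can relative dose intensity show what the rows miss? SAP 9.2 divides actual intensity by a planned value of 300 x 14 / 28 = 150 mg/day for every subject. For a full cycle:

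- 300x21: 6300 / 28 = 225 mg/day; 225 / 150 = 150%
- 200x21: 4200 / 28 = 150 mg/day; 150 / 150 = 100%
- 200x14: 2800 / 28 = 100 mg/day; 100 / 150 = 67%

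A cycle at 200x21, reached by a toxicity step down from 300x21, therefore reads as full planned intensity. The measure does not reveal that first step.

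Last, the dose-escalation tables in SAP 12.1 name two schedule periods, 300 mg x 14/28 and 300 mg x 21/28. A period at 200x21 has no category there. The fifth path never includes 300x21, so that subject does not meet the SAP's definition of escalation at all.

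**The case against.** The strongest reply is that little is hidden. The any-adjustment and AE-adjustment rows in SAP 9.3 cover any schedule, and time to first AE-related adjustment is also summarised. SAP 12.1 and 12.2.1 tabulate adverse events, and events of special interest, leading to dose reduction with no schedule limit, and subject listings support them. Exposure and adverse events on the 21-day regimen have their own analyses. Counting reductions only on the randomised 14-day regimen could also be defended as a descriptive choice, since subjects on 21 days have already relapsed.

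Most of this stands. A reader might infer that toxicity reductions on the 21-day schedule vanish from the report. They do not; they are lost only from two descriptive rows. What the reply does not supply is an output that gives the number of steps or the schedule reduced from. Nor does the SAP say that its rows are meant to be limited to the 14-day regimen.

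Three further inferences should be resisted.

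- **Size.** One could multiply assumed rates of escalation and later reduction by the 230 subjects planned per arm. The documents give neither rate, and such a product would count as missed some subjects who are already in the one-reduction row.
- **Direction.** One could expect the omission to fall mainly on azacitidine because of drug toxicity. But extension is triggered by relapse under the same blinded rule in both arms. If azacitidine delays relapse, placebo could supply more extended subjects. The documents do not settle it.
- **Repeat dose reductions.** A second 300-to-200 mg step after re-escalation might look like another miscount. On a plain reading it exceeds the protocol's limit of one dose reduction, so the point does not rest on it.

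Agreement with the AE-adjustment row is not a test either. The reduction rows are defined by regimen rather than by cause, so the two would differ anyway.

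**Conclusion.** The definitions in SAP 9.3 are wrong as written, and the matter is minor. Two descriptive exposure rows undercount or misclassify reduction steps for subjects who step down from a 21-day schedule. This follows from the wording of SAP 9.3 set against Protocol 8.2.5, Table 2 and 8.2.6. It assumes only that the rows are programmed as written. The number of subjects affected and the balance between arms cannot be determined from the documents. No efficacy endpoint, hypothesis test, alpha or power result is touched, and the adverse event tables are unaffected. No view is taken on any dosing rule; the need is that the SAP definition and Protocol 8.2.5 be reconciled.

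**What to change.** In SAP 9.3, replace the named regimens with a definition relative to the regimen in force:

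- a dose step is any decrease in assigned dose from 300 to 200 mg;
- a schedule step is any decrease in assigned schedule from 21 to 14 days or from 14 to 7 days;
- steps are counted per subject and shown by the schedule reduced from (14-day or 21-day).

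This changes no dosing rule and needs no new data. SAP 9.4 states that assigned dose is recorded on the CRF, and SAP 9.2 and 9.3 already rely on the assigned regimen. The cost is a short wording change and the reprogramming of one table.
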